6.14.2. Adverse Events

A treatment-emergent adverse event (TEAE) is defined as an event that first occurred or worsened in severity after baseline. The MedDRA Lowest Level Term (LLT) will be used in the treatment-emergent computation. The maximum severity for each LLT during the screening period will be used as baseline. The treatment period will be included as post-baseline for the analysis.

In an overview table, the number and percentage of patients who experienced a TEAE, serious adverse event, adverse event related to study drug, died due to an adverse event, or discontinued from the study due to an adverse event will be summarized by treatment. These summary tables will additionally be provided for the Induction, Maintenance and Extension Periods.

The percentages of patients with TEAEs will be summarized by treatment using MedDRA Preferred Term nested within System Organ Class. Events will be ordered by decreasing frequency within System Organ Class. As an additional table, the percentages of patients with TEAEs will be summarized by treatment using MedDRA Preferred Term (without regard to System Organ Class). Events will be ordered by decreasing frequency.

Adverse events considered possibly related to study drug by the investigator will be displayed using MedDRA Preferred Term nested within System Organ Class. Events will be ordered by decreasing frequency within System Organ Class.

Adverse events that start during the screening period will be summarized in listings..

Subgroup analysis by Prior Biologic exposure will be performed for the summaries described above. Prior Biologic use status for the purposes of subpopulation identification will be based on the 'Prior Biologic Y/N?' eCRF question.

Brief narratives of all patients experiencing a death, a serious adverse event, or an adverse event leading to study drug discontinuation will be provided.

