12.2.8. Safety Analyses

Safety will be assessed by evaluating all reported AEs and changes in laboratory analytes, ECGs, and vital signs (including body weight).

Duration of exposure to therapy will be calculated for each subject and summarized by treatment group.

AEs will be coded according to the *Medical Dictionary for Regulatory Activities* and summarized by system organ class, preferred term, severity, and relationship to investigational product. A TEAE is defined as an event that first occurred or worsened in severity after baseline. In the analysis of TEAEs during the induction period, all preexisting conditions recorded at screening (Visit 1) and any on-study AEs recorded at or before baseline (Visit 2) will be used as baseline. In the analysis of TEAEs during the maintenance period, any on-study AEs recorded at Week 12 will be used as baseline. The induction period and the maintenance period will be analyzed separately. For each event classification term, the number of subjects experiencing a TEAE with that classification term will be tabulated. Treatment-related TEAEs are defined as events that are indicated by the investigator on the CRF to be related to treatment. If a subject reports the occurrence of a particular event more than once, the most severe of those events will be included in the summary tables of TEAEs, and the most severe of the most related of those events will be included in the summary tables of treatment-related events. TEAEs of interest will be presented.

Additional safety parameters include laboratory test results, ECGs, and vital-sign measurements. The baseline for computing the change in safety variables for the induction period will be data collected at or before dosing on Visit 2; the baseline for the maintenance period will be the last value collected during the induction period. The parameters will be listed and summarized with standard descriptive statistics. Change from baseline will also be summarized by randomized treatment.

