6.14. Safety Analyses

All safety evaluations will be based upon the Safety Population as defined in Section 6.2.

Any statistical comparisons for safety data will be performed only between the “All LY3074828” treatment group and Placebo. No pairwise comparisons between LY3074828 induction treatment arms will be performed. Pairwise comparison of LY3074828 maintenance treatment arms will be performed (no comparison to placebo). No multiplicity control procedure will be performed for these tests of safety data.

Safety and tolerability will be evaluated in terms of treatment-emergent AEs (TEAEs), AEs leading to permanent discontinuations of study drug, SAEs, deaths, changes in clinical laboratory test results, and vital signs. These measures will be analyzed for each dose group and combined LY3074828 groups, separately for each study part, as well as across study parts for key summaries.

For all quantitative safety analyses, baseline is defined as the last non-missing assessment recorded on or prior to the date of first study drug injection at Week 0 (Visit 2). However, placebo patients who enter the Extension Period will have their baseline reset. Their new baseline will be defined as the last non-missing assessment on or prior to the date of first injection of study treatment at Week EW0 (Extension Visit 1).

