6.18. Changes to the Planned Analysis from the Clinical Study Protocol

The primary analysis method for categorical variables will now be logistic regression not CMH.

Prior Concomitant and Current Concomitant medication will not be summarized as reported in section 12.2.4 of the protocol. Prior Medication and Concomitant medications will be summarized per section 6.10 of the SAP.

As of the approval date of SAP version 3, there are no additional changes to the planned analysis in the protocol.

7. Unblinding Plan

A limited number of pre-identified individuals at Eli Lilly and Company may gain access to the unblinded data as part of the prespecified interim analysis (see section 6.17) in order to initiate the final population PK/PD model development processes for primary analyses and/or to evaluate safety data. Information that may unblind the study during the analyses will not be reported to study sites until the Maintenance period has been completed.

Additionally, a limited number of pre-identified individuals, an Eli Lilly and Company PK/PD Scientist and unblinded site pharmacists will have access to patients dosing information in order to conduct the TDM adjustments. Unblinded dosing information will not be shared with any other study or site personnel.

8. References

- [2] Frank-Bretz et al., Graphical approaches for multiple comparison procedures using weighted Bonferroni, Simes or parametric tests,, *Biometric Journal* 53 (2011) 6, 894-913. Al
- [2]. Mohamed Aloh et., Advanced multiplicity adjustment methods in Clinical trials,, *Statistics in Medicine*, Published on line 16 September 2013 in Wiley Online Library.
- [3]. Mosli M et al., Development and validation of a histological index for UC, *Gut* 2015, 0:1-9.
- [4]. Travis et al., Developing an instrument to assess the endoscopic severity of ulcerative colitis: the Ulcerative Colitis Endoscopic Index of Severity (UCEIS), *Gut* 2012, 535-42.

9. Appendices

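### The SAP judges maintenance-period TEAEs against screening, the protocol judges them against AEs recorded at Week 12, and SAP 6.18 does not list the change

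*SAP*

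**What the plan says.** **SAP 6.14.2** defines a TEAE as an event that starts or becomes more severe after baseline, computed at MedDRA Lowest Level Term (LLT). On the baseline: "The maximum severity for each LLT during the screening period will be used as baseline". On the window: "The treatment period will be included as post-baseline for the analysis". On the overview tables: "These summary tables will additionally be provided for the Induction, Maintenance and Extension Periods". No separate maintenance baseline is given there or elsewhere in the SAP for AEs.

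**Protocol 12.2.8** sets two TEAE baselines. Induction uses pre-existing conditions and AEs recorded up to Visit 2. For maintenance: "In the analysis of TEAEs during the maintenance period, any on-study AEs recorded at Week 12 will be used as baseline". It adds: "The induction period and the maintenance period will be analyzed separately".

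**SAP 6.14** has a baseline rule for measurements: "For all quantitative safety analyses, baseline is defined as the last non-missing assessment recorded on or prior to the date of first study drug injection". Its only reset is for placebo patients who enter the extension. The same section plans pairwise safety comparisons of the two maintenance arms.

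**SAP 6.18** names two departures from the protocol, logistic regression and the medication summaries, and then says that "there are no additional changes to the planned analysis in the protocol".

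**The concern.** A maintenance TEAE table should show what arose or worsened on the subcutaneous maintenance regimen. With a screening baseline, anything that appeared during intravenous induction is already above baseline when maintenance starts. A maintenance record of that term can then be called emergent even though it is no worse than at Week 12. The protocol's rule prevents this.

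The table matters because the Q4W and Q12W arms are to be compared on safety, and protocol 7.2 says these arms are there to support the choice of a maintenance regimen for later studies. A reader who relies on SAP 6.18 would not know that the baseline behind these tables differs from the protocol's.

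**Working it through.** **No plan figure to reproduce.** The documents state no AE rate, and the point turns on a definition.

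**Step 1: apply both rules to the same histories.** Let S, W and M be the severity of one LLT at screening, at Week 12 and in a maintenance record (0 none, 1 mild, 2 moderate). The SAP rule calls the record emergent if M > S; the protocol rule does so if M > W. Conditions still present at Week 12 are taken to be part of the Week 12 baseline.

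| History | S, W, M | SAP | Protocol |
|---|---|---|---|
| New in induction, unchanged | 0, 1, 1 | yes | no |
| New in induction, improving but present | 0, 2, 1 | yes | no |
| Mild at screening, worsened in induction, unchanged since | 1, 2, 2 | yes | no |
| New in induction, worse in maintenance | 0, 1, 2 | yes | yes |
| New in maintenance | 0, 0, 1 | yes | yes |
| Mild at screening, unchanged | 1, 1, 1 | no | no |
| Moderate at screening, gone by Week 12, returns mild | 2, 0, 1 | no | yes |

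The first three rows are emergent only under the SAP. The last row goes the other way: the SAP rule misses an event that the protocol rule counts. So the rates are misstated, and the direction is not upward for every history.

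**Step 2: does the record reach the maintenance table?** The SAP does not say whether an AE belongs to a period by its onset date or by being present in it. SAP 6.10 has a presence rule, but for concomitant medications only.

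- *Onset assignment.* A single continuous record that began in induction stays in the induction table, so the effect for unchanged ongoing AEs is zero. A separate maintenance record of a term already present at Week 12, at the same or lower severity but above its screening severity, is still classed differently by the two rules.
- *Presence assignment.* The continuous record also enters the maintenance table as emergent.

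**Step 3: illustrative size under presence assignment.** Assume a true maintenance any-TEAE rate p, a share q of patients with an induction-onset AE still present, and independence. Then reported rate = p + (1 − p)q.

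| p | q = 5% | q = 10% | q = 20% |
|---|---|---|---|
| 40% | 43% | 46% | 52% |
| 50% | 52.5% | 55% | 60% |
| 60% | 62% | 64% | 68% |

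For example, 0.40 + 0.60 × 0.05 = 0.43 and 0.40 + 0.60 × 0.20 = 0.52. For a single term with p = 3%, q of 1% gives 0.03 + 0.97 × 0.01 = 4.0%, and q of 3% gives 0.03 + 0.97 × 0.03 = 5.9%.

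**Step 4: effect on the arm contrast.** If q is the same in both arms, the reported difference is the true difference times (1 − q). With assumed true rates of 40% and 55% and q = 15%, the reported rates are 1 − 0.60 × 0.85 = 49% and 1 − 0.45 × 0.85 = 61.75%. The difference falls from 15 to 12.75 points.

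**The case against.** **The protocol rule may still govern.** SAP 6.14.2 states the screening baseline once, for an undivided treatment period, and only afterwards mentions tables by period. Since 6.18 disclaims further changes, one could read the protocol's Week 12 baseline as still applying. This does not hold: 6.14.2 gives a specific rule that conflicts with the protocol's and no exception for the period tables. A general disclaimer does not restore the other rule.

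**Assignment may be by onset.** A reader might infer that every induction AE continuing past Week 12 is counted again. The documents do not establish this. The cues in the AE text lean towards onset: SAP 6.14.2 describes screening-period AEs by when they start, and the anaphylaxis algorithm in 6.14.2.2 requires both events to begin within its window. They do not settle the period tables, but they make re-counting of a continuous record conditional. This part of the objection stands.

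**Re-randomisation protects the comparison.** LY3074828 responders are re-randomised to Q4W or Q12W, so carried-over AEs should be balanced on average. This also stands: the contrast may be diluted, but there is no systematic bias between the arms. An event that appears once in each of two period tables is not counted twice within either.

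**The extension is different.** A reader might extend the contradiction to placebo patients who start LY3074828 in the extension. The protocol sets no TEAE baseline for the extension, so the SAP contradicts nothing there. The Extension Week 0 reset in SAP 6.14 is written for quantitative safety analyses; whether it reaches AEs is arguable.

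**Conclusion.** The conflict between SAP 6.14.2 and protocol 12.2.8 is explicit, concerns the same analysis and is not declared in SAP 6.18. Under the SAP rule, terms first seen or worsened in induction and no worse than at Week 12 can be tabulated as maintenance-emergent, contrary to the protocol.

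The likely consequence is misstated maintenance TEAE rates and some dilution of the Q4W versus Q12W contrast. How far this goes depends on the unstated period-assignment rule. A reader might take the 49% and 61.75% above as an expected overstatement of 9 and 6.75 points; they are not, because they rest on assumed rates, independence and presence assignment. The documents support the direction for the histories shown, not a magnitude.

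This should be corrected, but it does not undermine the induction safety tables, for which the screening baseline is appropriate.

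**What to change.** In SAP 6.14.2:

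1. Keep the screening baseline for induction and for tables that combine induction with a later period.
2. For maintenance tables, use AEs present at Week 12 before the first subcutaneous dose, by LLT and severity, to match protocol 12.2.8.
3. State whether AEs are assigned to a period by onset or by presence.

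If the screening baseline is intended for maintenance, list it in 6.18 as a change from the protocol and give the reason.

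For placebo patients who enter the extension, an AE baseline at Extension Week 0 would parallel the reset in SAP 6.14. This is an improvement in consistency, not the repair of a protocol conflict.

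The cost is SAP wording and a derivation flag. The protocol schedule already collects AEs at Visits 7 and 8, so no new data are needed.

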Responding subjects who have received LY3074828 will be re-randomized to 1 of 2 LY3074828 maintenance treatment arms (200 mg every 4 weeks [Q4W] SC or 200 mg every 12 weeks [Q12W] SC); any subjects in the placebo arm achieving a clinical response will remain on placebo. The maintenance period is designed to explore the safety and durability of clinical responses and remissions to treatment with 200 mg LY3074828 administered SC Q4W or

[figure not shown]
Q12W. Subjects having clinical responses (see Section 10.1.2) at Week 12 will continue study participation in the maintenance period up to Week 104. Subjects who are randomized in the induction period but do not have a clinical response at Week 12 will have the option to continue in a study extension period (Section 7.1.1) or discontinue from the study.

Subjects entering the LY3074828 maintenance dosing period will be stratified according to their Week-12 remission status. After Week 52, subjects who experience worsening of UC (partial Mayo score of 7 or more) may receive rescue treatment with LY3074828 200 mg SC Q4W.

Maintenance Follow-Up Period (16 Weeks):

The follow-up period will include a visit every 4 weeks for a total of 16 weeks following Week 104 to assess subject safety.

Subjects who discontinue the study for any reason during the maintenance or maintenance follow-up period will complete the maintenance period early termination visit (V804).

Abbreviations: EOS = end of study; ET = early termination; IV = intravenous; LY = LY3074828; n = number of subjects; Q4W = every 4 weeks; Q12W = once every 12 weeks; SC = subcutaneous; W = study week.

Note: Induction nonresponders can consider participation in the study extension period (Section 7.1.1).

Figure AMAC.7.1. Protocol I6T-MC-AMAC study design.

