Extension Period- Induction: Patients who complete the study induction period (through Visit 7) but do not have a clinical response may choose to participate in the study extension period following consultation with, and at the discretion of, the investigator.

During the extension period induction, all patients are planned to receive 1000 mg LY3074828 IV administered at Extension Weeks 0, 4, and 8 (the dose level and/or frequency of dosing may

be reduced based on review of Study AMAC trial data). Patients should complete all assessments according to the extension period schedule of events and should remain on permitted UC concomitant medication according to Section 9.9 of the protocol.

[figure not shown]
Extension Period- Maintenance: Patients who have a clinical response (Section 6.11.3.1) at Extension Visit 6 will have the opportunity to continue on extension period maintenance therapy, while non-responders at Extension Visit 6 will be discontinued from the study.

Patients who continue into the extension period maintenance treatment are planned to receive unblinded 200 mg LY3074828 administered SC Q4W, should complete all assessments according to the extension period schedule of events in Attachment 2 of the protocol, and should remain on permitted UC concomitant medication according to Section 9.9 of the protocol. The dose level and frequency of dosing may be reduced based on review of Study AMAC trial data.

An addendum has been planned for sites that have subjects that need to extend treatment in study AMAC in order to have the opportunity to participate in an OLE (Open Label Extension) study (this is Country specific). The duration of the maintenance period and extension maintenance period will be extended to provide for up to an additional 52 weeks of therapy so that subjects can continue to receive study drug until the OLE Study becomes available. Once an OLE study becomes available, subjects will be asked to consider participation in the OLE or be discontinued from AMAC. Patients will continue to be followed for safety and clinical benefit during this additional year of therapy and in addition the sponsor conducts quarterly trial level safety reviews (TLRs) during the study. No TFLs or further analyses are planned for the addendum.

Figure 1 and Figure 2 show the study design.

Figure 1 Study Schematic (Induction and Maintenance Periods)

[figure not shown]

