separately for the Induction Dosing Period and the Maintenance Dosing Period. Summaries and analyses will be also presented for the Extension Period.

By-patient listings will be sorted by treatment allocation, site and visit. Numeric data will be listed to the same number of decimal places as recorded on the eCRF. For derived variables, the number of decimal places will be listed as specified. The decimal points will be aligned in the data listings. For the tables and listings in the appendices, "Page x of X" will appear on each page.

By-patient listing will be generated for each SDTM dataset. If necessary, separate listing for derived variables (that are derived from the SDTM datasets) will be generated. Wherever applicable, listings will include the period of the study during which the event or measurement occurred.

Efficacy analyses will be conducted on the Intent-to-Treat (ITT) population. All safety analyses will be conducted on the Safety Population. These populations are defined in section 6.2.

Patients will be analyzed according to the treatment to which they were assigned regardless of any errors of dosing.

All tests of treatment effects will be conducted at a 2-sided alpha level of 0.05 unless otherwise stated. Unless otherwise specified, no multiplicity adjustment will be considered for planned analyses.

For all efficacy and health outcomes analyses, baseline is defined as the last non-missing assessment recorded on or prior to the date of first study drug injection at Week 0 (Visit 2). However, placebo patients who enter the Extension Period will have their baseline reset. Their new baseline will be defined as the last non-missing assessment on or prior to the date of first injection of study treatment at Week EW0 (Extension Visit 1).

Unless otherwise specified, variables will be analyzed in the original scale on which they are measured. However, if it is deemed more statistically appropriate, a transformation, such as to the logarithmic scale, may be applied before analysis. The parametric approach will be employed by default for statistical analysis except when nonparametric analysis, such as by a rank-based method, is assessed to be more fitting.

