6.14.3. Deaths, Serious Adverse Events, and Other Significant Adverse Events

The number and percentage of patients who experienced a serious adverse event during the treatment period will be summarized by treatment using MedDRA Preferred Term nested within System Organ Class. Events will be ordered by decreasing frequency within System Organ Class.

These summary tables will be generated for the study overall and additionally will be generated for the Induction, Maintenance and Extension Periods.

In the event differential dropout rates are seen, summary tables comparing exposure-adjusted incidence rate (that is, person-time-adjusted incidence rates) over the entire time period will be generated for the Induction and Maintenance Periods for applicable safety evaluations of interest.

The number and percentage of subjects who permanently discontinued from study treatment due to an adverse event (including adverse events that led to death) during the treatment period will be summarized by treatment using MedDRA Preferred Term nested within System Organ Class. Events will be ordered by decreasing frequency within System Organ Class.

A listing of deaths will be provided. All deaths will be included, regardless of the Investigator's or the Sponsor's judgment about causality, including (1) any deaths occurring during participation of the study, (2) any deaths occurring after a patient leaves (i.e., discontinued from the study or completes the study) if the death is the result of a process initiated during the study, regardless of when it actually occurs. Each listing will include investigator ID, patient ID, treatment group, baseline age, sex, associated AE, whether or not the death and Lilly's assessment of whether the process leading to death (NOT the death itself) began:

- "On study": during study or within the 24-hour day after day of last dose in study.
- "Shortly after study": from the end of the "On Study" time period to 4 weeks after last dose in study or
- "Long after study": more than 4 weeks (or longer, as specified in "Shortly After Study") after the last dose in study

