6.14.4. Clinical Laboratory Evaluation

Laboratory evaluations will be summarized and analyzed for the following periods:

- Induction Period,
- Maintenance Period,
- Extension Period (including Extension Induction and Extension Maintenance)

Laboratory tests include all planned analytes as defined in the protocol, excluding those collected in a reflex manner (only collected under certain circumstances).

Values at each visit (starting at randomization) and change from baseline to each visit for laboratory tests will be displayed in box plots (notched box for each treatment with outliers displayed) for patients who have both a baseline and a result for the specified visit. Individual measurements outside of reference limits (defined by the performing laboratory) will also be displayed using distinct symbols overlaying the box plot. Baseline will be the last non-missing observation in the screening period. Original-scale data will be used for the display. Unplanned measurements will be excluded. Displays using both SI and U.S. conventional units will be provided (when different). The following summary statistics will be included in a table below the box plot: N, mean, standard deviation, minimum, Q1, median, Q3, and maximum. Box plots will be used to evaluate trends over time and to assess a potential impact of outliers on central tendency summaries.

Change from baseline to last observation will also be summarized within the box plot of changes (rightmost column) for patients who have both baseline and at least one post-baseline result. Baseline will be the last non-missing observation in the screening period. The last non-missing observation in the treatment period will be used as the last observation. Original-scale data will be used. Unplanned measurements will be excluded. A p-value will be included in the summary statistics at the bottom of the box plot for this assessment, using an ANCOVA model containing terms for treatment and the continuous covariate of baseline measurement.

For quantitative laboratory analyte measurements, 3-panel displays that include a scatterplot, a shift table, and a shift to high/low table will be created. Specifically, for each measurement, both a 3-panel display assessing low values and a 3-panel display assessing high values will be created.

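### The SAP ties TEAE counting to an undated treatment period and plans no summary of the 16-week follow-up or the addendum; its SAE text conflicts on whether follow-up counts

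*SAP*

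**What the plan says.** SAP 6.14.2 defines a TEAE as an event that begins or worsens after baseline, takes the worst severity in screening as that baseline, and then states "The treatment period will be included as post-baseline for the analysis". For the overview table it adds "These summary tables will additionally be provided for the Induction, Maintenance and Extension Periods". It gives no end date for the treatment period and no lag after the last dose.

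SAP 6.1 lists a Follow Up Period among the study periods. Table 1, which assigns groups and populations to each treatment period, has rows only for induction, maintenance and the two extension parts. Summaries are to be presented "separately for the Induction Dosing Period and the Maintenance Dosing Period", and also for the extension.

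SAP 6.14.4 lists the laboratory periods as Induction, Maintenance and "Extension Period (including Extension Induction and Extension Maintenance"). SAP 6.14.5 names the same three for vital signs.

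On SAEs, SAP 6.14.3 first says "The number and percentage of patients who experienced a serious adverse event during the treatment period will be summarized by treatment". Its next paragraph says "These summary tables will be generated for the study overall and additionally will be generated for the Induction, Maintenance and Extension Periods".

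Protocol 7.1 gives the purpose of follow-up: "The follow-up period will include a visit every 4 weeks for a total of 16 weeks following Week 104 to assess subject safety". Protocol 7.1.1 plans the same after Extension Week 92. Attachments 1 and 2 schedule AE collection and vital signs at every follow-up visit, and hematology and chemistry at some of them.

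SAP 5.1 describes a country-specific addendum with up to 52 more weeks of study drug, and says of it: "No TFLs or further analyses are planned for the addendum".

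**The concern.** Safety and tolerability is the first secondary objective. The last injection coincides with the last maintenance visit, so a counting window that closes with the treatment period closes on the day of the last dose. Whatever first appears afterwards falls in a period for which no incidence summary is named, although the visits were scheduled to look for it.

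The SAP is also narrower than the protocol without saying so. The protocol's glossary definition of a TEAE has no end date, and protocol 12.2.8 evaluates every reported AE. SAP 6.18, which records departures from the protocol's planned analysis, does not mention a narrower window.

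The SAP's own windows do not match one another. The deaths listing in 6.14.3 recognises an interval of up to 4 weeks after the last dose. Immunogenicity in 6.14.8.2 runs open-ended from the first dose. TEAEs have neither, yet 6.14.8.4 tabulates TEAEs by ADA status.

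At stake are the completeness of the TEAE incidence tables for the longest-treated patients, and whether two programmers working from 6.14.3 would produce the same SAE counts.

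**Working it through.** **Length of follow-up (Attachments 1 and 2).**
- Maintenance: Week 120 − Week 104 = 16 weeks; Day 840 − Day 728 = 112 days = 16 weeks.
- Extension: Week 108 − Week 92 = 16 weeks; Day 757 − Day 645 = 112 days = 16 weeks.

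Both reproduce the protocol's stated 16 weeks.

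**Last doses (SAP 5.3; protocol Table AMAC.1; Attachments).**
- Maintenance Q4W, from Week 12: 12 + 23 × 4 = Week 104.
- Maintenance Q12W, from Week 12: 12 + 7 × 12 = Week 96 for the last active dose. The next would fall at Week 108, and the Week 104 injection in this arm is placebo.
- Extension Q4W, from Extension Week 12: 12 + 20 × 4 = Extension Week 92.

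**Part of the last active dosing interval that lies in follow-up.**

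| Regimen | Interval (weeks) | Up to last maintenance visit | In follow-up | Share |
|---|---|---|---|---|
| Maintenance Q4W | 104–108 | 0 | 4 of 4 | 100% |
| Maintenance Q12W | 96–108 | 8 | 4 of 12 | 33% |
| Extension Q4W | 92–96 | 0 | 4 of 4 | 100% |

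**Drug remaining.** Protocol Section 5 gives a half-life of about 10 days. With simple exponential decline (an assumption that ignores SC absorption and accumulation), the fraction left t days after a dose is 2^(−t/10).
- Q4W at day 28: 2^(−2.8) = 14%. At day 56: 2^(−5.6) = 2%.
- Q12W on entering follow-up, 104 − 96 = 8 weeks = 56 days after its last active dose: 2%.

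The argument that drug is still present therefore applies mainly to the Q4W regimens and to the first weeks of follow-up.

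**Share of scheduled observation.** For a maintenance completer, 16/120 = 13.3% of Weeks 0–120, or 16/(120 − 12) = 14.8% of the time after Week 12. For an extension completer, 16/108 = 14.8% of extension time.

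**Person-time.** N patients completing follow-up contribute N × 112/365.25 patient-years. The documents do not give N. Taking 30 to 120 as an assumption only, this is 9.2 to 36.8 patient-years. No event rate is given, so no event count follows.

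**Does the text place follow-up outside the counted time?**

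| Output | Text pointing to exclusion | Text pointing to inclusion |
|---|---|---|
| TEAE tables | 6.14.2 treatment-period sentence; no follow-up row in Table 1 | TEAE definition has no end date; an overall overview table is implied |
| SAE tables | 6.14.3, first sentence | 6.14.3, tables for the whole study; 6.14, key summaries across study parts |
| Labs, vital signs | Period lists in 6.14.4 and 6.14.5 | None for maintenance follow-up |
| Extension follow-up | SAP 6.1 lists follow-up separately | Attachment 2 heads V805–V808 as part of the Extension Period |
| ADA | None | 6.14.8.2 and 6.14.8.4 use all observations after first dose |
| Addendum | SAP 5.1 rules out tables, figures and listings | None |

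**The case against.** The case on the other side is substantial.

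- **The TEAE sentence may not be a restriction.** It says the treatment period counts as post-baseline, in contrast to screening; it does not say follow-up is excluded. Because the period tables are described as additional, an overall overview table is implied, and its SAE and death rows are not expressly limited to TEAEs. This stands as ambiguity. It does not supply an end date or a follow-up table.
- **SAEs.** A reader might infer that an SAE two weeks after the final injection enters no table. The documents do not establish that, because 6.14.3 also calls for tables over the whole study. What remains is a contradiction within one section.
- **Nothing is lost from the report.** SAP 6.1 promises a by-patient listing of every dataset. SAP 6.14.2 promises narratives for all deaths and SAEs, and the deaths listing runs past the last dose. The ADA tabulation has an open-ended window. All of this is right: the gap is in incidence tables, not in capture. The late hypersensitivity window in 6.14.2.2 ends at the next dose, so it has no stated end after the last one, but it counts only TEAEs and inherits the same doubt.
- **On-treatment incidence is legitimate.** Adding off-drug weeks to the Q4W versus Q12W comparison could dilute it. This is accepted, and the fix leaves that comparison alone.
- **Reach.** Only patients who get to Week 104 or Extension Week 92 have the scheduled follow-up. Early discontinuers have an early termination visit, and protocol 7.2 allows patients entering follow-up to consider an open-label study instead.
- **The addendum choice is disclosed,** with safety follow-up and quarterly trial-level reviews continuing. Those reviews are not reported incidence.

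**Conclusion.** The point holds as a gap in definition and planning. Read literally, TEAEs arising after the last injection are not counted in the TEAE incidence tables: all 4 weeks of the last dosing interval for both Q4W regimens, 4 of 12 weeks for the last active Q12W dose, and the remainder of the 16-week follow-up. Laboratory and vital-sign summaries omit the maintenance follow-up by their own period lists. For the extension follow-up the documents point both ways. Up to 52 weeks of further active treatment are expressly left out of all tables, figures and listings.

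Three stronger conclusions are not supported. Exclusion of follow-up SAEs is possible but not shown. The whole interval after the last active Q12W dose is not lost, since 8 of its 12 weeks precede follow-up. Nor can one say that reported incidence will be too low by any given amount: the number entering follow-up and the event rates there are not stated.

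The conclusion rests on reading the treatment period as the dosing periods in SAP Table 1, and on patients completing dosing as scheduled. It is a worthwhile, inexpensive correction that leaves the primary efficacy analysis untouched.

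**What to change.** 1. In SAP 6.14.2 and 6.14.3, state that the overall TEAE and SAE tables run from first dose to the last study visit (V804, V808 or early termination), and give dates to the treatment period used in the period tables.
2. Reconcile the two SAE sentences in 6.14.3 so that only one count is possible, and say whether extension follow-up belongs to the Extension Period.
3. Keep the on-treatment period tables and the Q4W versus Q12W safety comparison as they are.
4. Add a separate Follow-Up Period table of TEAEs, SAEs, laboratory results and vital signs by last assigned regimen.
5. Replace the SAP 5.1 sentence on the addendum with a final cumulative table of addendum AEs, SAEs and exposure.
6. Record the TEAE window in SAP 6.18 if it is to stay narrower than the protocol's definition.

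The cost is SAP wording and a few more table programs. The scheduled follow-up data are already collected, and no visit or procedure is added. Reported incidences in the overall tables may rise slightly; the on-treatment figures do not change.
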